#### 4.3.5 Assessment of the nasal tolerability

Nasal tolerability/irritation will be assessed for all patients based on combined participant reported symptoms and investigator examination/inspection of the nasal cavities. The symptoms and signs can include sneezing, redness, itching, nasal discharge, local tenderness, swelling or other nasal irritation. Nasal tolerability/irritation will be assessed at 30- and 60-min post IMP administration (following pain, sedation and vital sign assessments). The 30 and 60 minute nasal tolerability timepoints should be taken from the *last* dose of IMP i.e. if a second dose of IMP is required, nasal tolerability should then be performed 30 and 60 minutes from the second dose. Any unpleasant symptoms from the nose during or after administration of the IMP reported by the participant will be recorded as adverse events.

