### 3.2 Exclusion Criteria

To participate in the study potential participants must not meet any of the following exclusion criteria:

1. Critical, life- or limb-threatening condition requiring immediate management.
2. Open fractures.
3. Participants with chronic pain.
4. Participants requiring oxygen therapy.
5. Clinically evident respiratory depression.
6. Clinically evident cardiovascular instability (e.g. pathological arrhythmia).
7. Known liver disease.
8. Known kidney disease.
9. Presence of other acute clinical or medical condition that may, in the opinion of the investigator, put the potential subject at risk when participating in the study, impact the participant's ability to participate in the study, or have impact on the study results, including being subject to head injury and / or altered consciousness.
10. A female of childbearing potential is eligible to participate if she verbally confirms not to be at risk of being pregnant or breastfeeding and agrees to follow the contraceptive guidance for 7 days after IMP administration.
11. Acute intoxication with drugs or alcohol, based on the judgement of the attending physician.
12. Participant showing abnormal nasal cavity/airway such as:
  - a. major septal deviation
  - b. evidence of previous nasal disease or surgery
  - c. current significant nasal congestion due to common cold
13. History or presence of hypersensitivity or allergy to sufentanil or ketamine, a history of anaphylactic reactions, or a history of other allergy that, in the opinion of the investigator, contraindicates their participation.
14. Has received treatment with sufentanil and/or ketamine during the last 72 hours
15. Is currently participating in or has participated in an interventional clinical trial with an investigational compound or device in the 4 weeks prior to signing the informed consent/assent for this trial.
16. Previous enrolment in the present study.

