### Part 2; Baseline and IMP treatment (Day 1)

The baseline assessment will include a repeat pain score, sedation score, and measurement of the participant's vital signs (respiratory rate, pulse rate, oxygen saturation) if not already undertaken at

the routine triage assessment. Once the pre-treatment assessments are performed the IMP will be administered.

After administration of IMP, pain scores will be assessed at the following approximate intervals (10, 15, 20, 30, 45, 60 min post IMP), as specified in the Study Assessment Chart (Table 1). The actual timepoints for pain assessment relative to IMP administration will be recorded in the eCRF.

Unscheduled pain intensity scores will be measured and documented during any potentially painful intervention (e.g. during the application of a plaster cast for a fracture), prior to rescue medication or prior to premature study withdrawal.

Where pain relief at 10-15 min after the first IMP administration is insufficient (for example, a pain score >4/10 on NRS, or at the discretion of the treating investigator), a second IMP dose of similar strength and dose can be administered to the participant. In the case of insufficient pain relief after two doses of IMP, additional analgesic medication may be administered at the discretion of the treating investigator, in accordance with standard local practice. The medication, dose and time of administration will be recorded in the eCRF.

After administration of IMP, level of sedation, vital signs (pulse rate, peripheral oxygen saturation, respiratory rate), nasal tolerability and spontaneously reported adverse events will be assessed.

Pain scores and safety assessments should continue for 60 min after the last dose of IMP, or until additional analgesic treatment or procedures need to be initiated. For further guidance on assessments at the treatment and post-treatment visit (Part 2), see Study Assessment Chart, Table 1.

Feasibility and treatment satisfaction in relation to the IMP and route of administration will be assessed prior to ED discharge.

Treatment satisfaction will be addressed by using the following standardized question: *“How satisfied are you with the study drug that you/your child received? Please think about how it helped their pain, how it was given, any side effects, and how quickly you/your child recovered”*. Respondents will answer using a 5-point Likert scale (very unsatisfied, unsatisfied, neutral, satisfied, very satisfied).

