- c) IMP will be administered to the participant while sitting in an upright position using the appropriate strength depending on the participant's weight. See more info in the IMP section and in the IMP manual.
- d) Adverse events will be collected spontaneously at all visits using open questioning.
- e) Nasal tolerability and irritation will be assessed using combined participant reported symptoms and investigator examination/inspection of the nasal cavities. Nasal tolerability will be performed twice; appr 30 min and 60 min after the *last* IMP administration (following pain, sedation and vital signs assessments).
- f) Treatment satisfaction will be addressed by asking the standardized questions "*How satisfied are you with the study drug that you/your child received? Please think about how it helped their pain, how it was given, any side effects, and how quickly you/your child recovered*". Respondents will answer using a 5-point Likert scale (very unsatisfied, unsatisfied, neutral, satisfied, very satisfied). Feasibility (i.e. acceptance of nasal administration) will be addressed by the healthcare staff asking the child: *If you were in this situation again*

and needed pain medication, would you like to receive the nasal spray? If not possible by the child, the parent/legal guardian will assess nasal acceptability.

g) Any medication given for AEs during the time from enrolment to follow up should be entered in the eCRF. Any 'rescue medication' (described as additional analgesics due to insufficient effect of IMP during the 60 min after the last dose of IMP), should be entered in the eCRF. The time given should also be noted.

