### 6.2 Assessment of safety and tolerability

#### 6.2.1 Primary safety and tolerability variables

To investigate the safety and tolerability of IN CT001 in pediatric participants in the acute care setting experiencing pain of moderate or severe intensity.

- Sedation as assessed by sedation score on the University of Michigan Sedation Scale (UMSS) (Malviya et al, Anesthesiology 2004) at the following timepoints: baseline and 10, 15, 20, 30, 45 and 60 min after first IMP administration. If a second IMP dose is needed, sedation will be performed at the timepoints relative to first IMP administration.
- Respiratory depression, assessed by respiratory rate.
- Peripheral Oxygen saturation, as assessed by peripheral oximetry.
- Cardiovascular stability, as assessed by pulse rate.
- Number of reported Adverse Events, graded by intensity and severity.
- Number of AEs reported per participant.
- Local nasal irritation as assessed by combined participant and investigator feedback at 30 and 60 min post IMP administration.

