### 6.3.2 Definitions of Adverse Events

#### **Adverse Event (AE):**

An AE is any untoward medical occurrence in a clinical study participant administered a pharmaceutical product and which does not necessarily have a causal relationship with this treatment. An AE can therefore be any unfavourable and unintended sign (including clinically significant abnormal values from relevant tests, such as clinical safety laboratory tests, ECGs, vital signs), symptom, or disease temporally associated with the use of an IMP, regardless of whether it is considered related to the IMP.

A baseline symptom is any medical event in a clinical study subject that occurs after he/she signed the ICF up until the first administration of IMP.

A treatment emergent AE (TEAE) is any AE not present, prior to the initiation of IMP administration or any event already present that worsens in either intensity or frequency following exposure to the IMP.

Only TEAEs are collected in this study (i.e., events occurring between screening and the first IMP administration are regarded as baseline symptoms and should not be recorded in the AE log in the eCRF).

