##### **Nasal irritation/Tolerability**

– The number of participants with nasal irritation will be summarised using counts and percentages of participant for each timepoint (30 and 60min post IMP administration) by age groups, dose level, and type of nasal irritation. A 95% CI of the percentage will be computed and reported.

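### Nasal irritation, a primary tolerability variable, has no recorded pre-dose score, so signs already present cannot be separated from effects of the spray in the planned table

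*Combined protocol and SAP*

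**What the plan says.** Section 6.2.1 lists among the primary safety and tolerability variables: "Local nasal irritation as assessed by combined participant and investigator feedback at 30 and 60 min post IMP administration". Section 4.3.5 sets the timing: "Nasal tolerability/irritation will be assessed at 30- and 60-min post IMP administration (following pain, sedation and vital sign assessments". Note e to Table 1 agrees: "Nasal tolerability will be performed twice; appr 30 min and 60 min after the" last administration. Section 4.3.5 describes what is looked for: "The symptoms and signs can include sneezing, redness, itching, nasal discharge, local tenderness, swelling or other nasal irritation".

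No nasal item appears before dosing. Section 4.2, Part 2, begins its list with "The baseline assessment will include a repeat pain score, sedation score, and measurement of the" vital signs, and the nose is not mentioned. Exclusion 12 does require a view of the nose ("Participant showing abnormal nasal cavity/airway such as", followed by three examples), but the protocol does not specify a nasal inspection for it and schedules no nasal score at that point.

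The analysis in section 7.4.1 is: "The number of participants with nasal irritation will be summarised using counts and percentages of participant for each timepoint", broken down by age group, dose level and type of irritation, with a 95% CI. It has no baseline, change, new-onset or relatedness rule.

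**The concern.** Section 1.7.1 gives the purpose of the nasal assessment: to make sure that the product does not irritate the nasal lining. That is a statement about the drug. The Protocol Outline gives the control as none, so the only reference available within the trial is each child's own state before the spray, and that state is not recorded.

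The plan treats its other repeated tolerability measures differently. Sedation has a pre-dose value (section 4.3.3). Vital signs have a pre-dose value (section 4.3.4) and an analysis of change from baseline (section 7.4.1). No reason is given for treating the nose differently.

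The signs in question are not specific to a nasal spray. The participants are injured children with moderate or severe pain, and in the group aged 1 to under 5 years crying is one of the five items of the pain scale (Appendix C). Discharge or redness before dosing is therefore plausible, although the documents do not say how common it is.

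At stake is whether the nasal percentage can be read as a property of CT001. The adverse-event data are also touched. Section 4.3.5 sends unpleasant nasal symptoms reported by the participant to the adverse-event log, and section 6.3.2 collects only treatment-emergent events: "A treatment emergent AE (TEAE) is any AE not present, prior to the initiation of IMP administration", or present and then worsened. Applying that definition needs knowledge of the nose before the spray.

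**Working it through.** The plan states no expected rate and no sample-size reasoning for nasal irritation. Its only design calculation concerns the responder rate and does not bear on this point. The check is therefore whether the planned data can identify a spray effect, followed by an illustration of size.

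**Inputs**
- N = 150 (Protocol Outline and section 7.1), and a minimum of 20 in the group aged 1 to under 5 years (section 5.4).
- b = share of children with signs before dosing that are still present at the assessment. The documents give no figure. *Assumption, range 0 to 30%.*
- t = share with irritation caused by the spray. The documents give no figure. *Assumption, range 0 to 10%.*
- b and t are taken as independent, and signs that start after dosing for other reasons are ignored. Section 7.4.1 asks for 95% intervals without naming a method; exact (Clopper-Pearson) intervals are used here.

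**Step 1: can the table identify t?** The expected reported proportion is a = 1 − (1 − b)(1 − t). The table estimates a only, which is one equation in two unknowns. Three different situations give the same result at N = 150:

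| b | t | a | Reported count (95% CI) |
|---|---|---|---|
| 0% | 10% | 10% | 15/150 (5.7 to 16.0%) |
| 5% | 5% | 1 − 0.95 × 0.95 = 9.75% | 15/150 (5.7 to 16.0%) |
| 10% | 0% | 10% | 15/150 (5.7 to 16.0%) |

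The planned data cannot tell them apart.

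**Step 2: how large could it be?** Take the case where the spray causes nothing, t = 0, so that a = b:

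| Assumed b | Raw post-dose count (95% CI) | New-onset count (95% CI) |
|---|---|---|
| 0% | 0/150 (0 to 2.4%) | 0/150 (0 to 2.4%) |
| 5% | 8/150 (2.3 to 10.2%) | 0/150 (0 to 2.4%) |
| 10% | 15/150 (5.7 to 16.0%) | 0/150 (0 to 2.4%) |
| 20% | 30/150 (13.9 to 27.3%) | 0/150 (0 to 2.4%) |
| 30% | 45/150 (22.8 to 38.0%) | 0/150 (0 to 2.4%) |

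The upper limit for 0/150 is 1 − 0.025^(1/150) = 2.4%. In the youngest group at its minimum of 20, b = 30% would show 6/20 (11.9 to 54.3%), against 0/20 new onset (0 to 16.8%).

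**Step 3: does the entry pain score imply crying?** Entry in the youngest group needs a FLACC score of 5 or more. The four items other than Cry can sum to 4 × 2 = 8, so a child can qualify without crying. Only a total of 9 or 10 forces a Cry score of at least 1. Crying before dosing is plausible but not guaranteed, which is why b is shown as a range that includes zero.

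**The case against.** There is a fair case on the other side.

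*The table makes no causal claim.* A reader might infer that the plan attributes every post-dose sign to the spray. It does not. Section 7.4.1 is descriptive, and section 4.3.5 gives examples of signs that feed a combined participant and investigator judgement. An investigator who saw the child before dosing may decide that a runny nose is not irritation. This stands. What remains is that the judgement rests on no recorded reference.

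*The adverse-event route already separates old from new.* A reader might infer that nasal symptoms cannot be classed as treatment-emergent. That goes too far. The protocol defines treatment-emergent events, keeps a log of baseline symptoms (section 6.3.1), grades causality (section 6.3.2.2) and tabulates relationship to treatment (section 7.4.1). Classification is possible. However, the baseline-symptom window opens only at consent, none of these steps requires a nasal examination, and none is linked to the nasal table.

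*Exclusion 12 removes abnormal noses.* Its list is illustrative, so it may reach beyond the three named conditions, and exclusion 9 gives further discretion. Neither clearly covers mild discharge or redness from crying.

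*Little depends on the figure.* All analyses are descriptive (section 7.4), no threshold rests on the nasal percentage, and any bias makes the product look worse. The breakdown by age group and type also lets a reader view discharge or redness separately. This limits the importance of the point but does not make the percentage interpretable as a drug effect.

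**Conclusion.** The point holds as a modest, cheap improvement. Followed exactly, the plan produces a nasal irritation percentage in which background and spray effect cannot be separated, for a variable the protocol names as primary for tolerability, and in a trial with no other reference. Sites would also apply the treatment-emergent definition to nasal symptoms without a structured pre-dose record.

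The direction is towards overstating irritation. The size is unknown. With no spray effect, the excess runs from none to about 45 of 150 as the assumed background runs from 0 to 30%. Those figures rest on an assumed background, on persistence of the signs to the assessment, on investigators scoring them as irritation, and on no unrelated new signs after dosing. No single inflation figure should be quoted as an estimate.

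The point does not show that the plan misattributes signs, that adverse-event classification fails, or that the safety conclusion would be too favourable.

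**What to change.** 1. In section 4.3.5 and Table 1 note e, add one recording of the same sign and symptom checklist before the first dose, made alongside the judgement for exclusion 12. It must precede the first dose, because the later assessments are timed from the last one.
2. Section 4.3.5 gives the signs no grade. Add a simple grade to the checklist so that worsening can be derived; without one, only new signs can be reported.
3. In section 7.4.1, report participants with new or worsened signs at 30 and 60 min, with the 95% CI, together with the raw counts already planned.

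The separate SAP foreseen in section 7 could add the analysis rule, but it cannot supply a pre-dose record that was never collected, so the collection change belongs in the protocol and eCRF.

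The cost is one eCRF entry and one extra table line, with no change to the sample size. The downside is a brief extra look at a distressed child before dosing. The checklist should be kept short so that analgesia is not delayed, a concern the protocol itself raises in section 1.8. Without a control group, new-onset signs may still include some unrelated to the spray, and the report should say so.

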#### 4.3.6 Assessment of medication errors

Medication errors will be assessed by feedback from site staff that administer the IMP. If they eg do not switch between nostrils when dosing CT001, or give a different number of sprays than required per IMP manual.

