Duration of Treatment	Patients will receive a single dose of CT001, with the option of a second dose after 10-15 min where sufficient analgesia is not achieved after first dose. Efficacy, safety monitoring, including measurement of vital signs will continue for 60 min. after the last dose or until rescue medication or procedures are initiated.
Control(s)	None

Primary Objectives	Endpoints	Assessments
To assess the safety and tolerability of CT001 in pediatric participants with moderate to severe pain in an acute care setting	The number and proportion (%) of participants with AEs  Number of AEs, graded by severity, and number of SAEs.	Pulse rate, Respiratory rate Peripheral oximetry Nasal irritation: (Combined participant and investigator reported nasal symptoms will be collected from all patients) Sedation: (The University of Michigan Sedation Scale (Malviya et al, Anesthesiology 2004)) Unsolicited adverse events (incl CNS AE's)
To evaluate the analgesic effect of CT001 in pediatric participants with moderate to severe pain in an acute care setting	Number and proportion (%) of participants that respond to the treatment relative to baseline (i.e. reduction in pain score to 4 or below) at 15 min post IMP administration.  Number and proportion (%) of participants that respond to the treatment relative to baseline (i.e. reduction in pain score to 4 or below) within 30 min post IMP administration.	Pain intensity score: For age group $\geq$ 1 year to $<$ 5 years FLACC score (assessed by site staff). For age group $\geq$ 5 years up to 9 years visual analogue scale modified with Wong-Baker faces For age group 9 to $<$ 18 years Numerical Rating Scale (NRS) 0-10.

Secondary Objectives	Endpoints	Assessments
To assess medication errors in pediatric participants with moderate to severe pain in an acute care setting	Number of medication errors	Type of medication errors (will be obtained via feedback from site staff that administer the IMP)

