### **Secondary objectives:**

- To assess medication errors in pediatric participants with moderate to severe pain in an acute care setting. (To be provided by site staff administering the IMP)
- To evaluate other analgesic effect of CT001 in pediatric participants with moderate to severe pain in an acute care setting.
- To evaluate the need of supplemental analgesics.
- To evaluate feasibility of CT001 in pediatric participants with moderate to severe pain in an acute care setting.

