## 5.5 IMP Accountability

All IMP for this study must be always retained in a safe place. Only personnel authorised by the PI at the site should dispense and administer the IMP. The investigator or pharmacist must complete an IMP accountability log, documenting product dispensed and used. This will be verified by the study monitor prior to destruction. Remaining IMP will be sent for destruction at the local hospital pharmacy, and this will be documented with a destruction certificate. If local pharmacy cannot destroy IMP, it can be returned for destruction according to the IMP manual.

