### 6.2.2 Secondary safety and tolerability variables

To evaluate the feasibility/treatment satisfaction of the nasally administered CT001 for acute pain relief in pediatric participants in the emergency setting.

- Treatment satisfaction as assessed by responses to the question: *“How satisfied are you with the study drug that you/your child received? Please think about how it helped their pain, how it was given, any side effects, and how quickly you/your child recovered”*. Respondents will answer using a 5-point Likert scale (very unsatisfied, unsatisfied, neutral, satisfied, very satisfied).
- Feasibility (i.e. acceptance of nasal administration) will be addressed by the healthcare staff asking the child: *If you were in this situation again and needed pain medication, would you like to receive the nasal spray (relative to an injection, tablet or suppository for the pain)?* If not possible by the child, the parent/legal guardian will assess nasal acceptability. Answers will be “yes”, “no”, “I don’t know”.
- Medication errors, defined as any deviation in the IMP administration instructions that result in higher or lower dose than planned. Examples may include erroneous priming of the pump, too few/many pumps administered, etc.

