**Overdose:**

Is a dose administered to a participant that exceeds the dose prescribed to that participant. Any overdose (and associated symptoms) must, at a minimum, be recorded as a non-serious adverse event.

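### Medication errors are taken from the feedback of the staff who give the dose, with no stated check against weight or product used, so unrecognised dosing errors may be missed

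*Combined protocol and SAP*

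**What the plan says.** The source of the data is given in three places, and it is the same in each:

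- Section 4.3.6: "Medication errors will be assessed by feedback from site staff that administer the IMP".
- Protocol Outline, secondary objectives table: the endpoint is "Number of medication errors" and the assessment is "Type of medication errors (will be obtained via feedback from site staff that administer the IMP").
- Section 2, first secondary objective: "To be provided by site staff administering the IMP".

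The definition is in section 6.2.2: "any deviation in the IMP administration instructions that result in higher or lower dose than planned". Section 7.4.2 then summarises such deviations as counts and percentages by age group and dose level.

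The planned dose depends on weight. Table 1, footnote c, reads "IMP will be administered to the participant while sitting in an upright position using the appropriate strength" and makes that strength a function of the child's weight. Section 5.3 refers to the Table 2 dosing chart and to a separate IMP manual.

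Other records bear on the dose given. Section 4.3.8 has weight measured, or estimated where weighing is impractical. Under section 5.5 the investigator or pharmacist "must complete an IMP accountability log, documenting product dispensed and used", and the monitor verifies that log. Section 8.7 has the monitor check IMP handling and verify source data. Section 6.3.2 states: "Any overdose (and associated symptoms) must, at a minimum, be recorded as a non-serious adverse event".

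**The concern.** The definition is objective, but the named measurement is subjective. To know that a dose was above or below plan, one must compare what was given with what the chart requires at that weight. Someone who has misread the chart or picked up the wrong strength may believe the dose was correct and so have nothing to report. Feedback is therefore weakest for the dose-changing errors that section 6.2.2 is meant to count.

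The count shows how reliably the spray can be dosed in an emergency department. If errors are under-recognised, a low count could reflect good dosing or poor detection, and the reader could not tell which. There is also a smaller effect on a primary endpoint: section 6.3.2 requires any overdose to be recorded at least as a non-serious adverse event, so an unrecognised overdose without symptoms may be missing from the adverse-event data as well.

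**Working it through.** The plan states no expected error rate, threshold or power for this endpoint, so there is no figure to reproduce. The check is a reading of the sections against each other, followed by an illustration on assumed values.

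**1. What a complete count needs, and what the plan links to it**

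| Needed | Where it stands | Linked to the endpoint? |
|---|---|---|
| Weight | Section 4.3.8 | No |
| Required strength and sprays | Table 2 and IMP manual (section 5.3) | Only through the staff's own awareness |
| Strength and sprays given | No visible sentence requires them in the eCRF per dose | Not stated |
| Product dispensed and used | Section 5.5 log, verified by the monitor | No |
| IMP handling, source data verification | Sections 7.5 and 8.7 | No |
| Overdose recorded as an adverse event | Section 6.3.2 | No |

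Section 4.3.7 does require the type, dose and time of rescue medication in the eCRF; no matching sentence for the IMP is visible. Section 7.4 reports several results by dose level, so some record of the dose must exist.

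**2. What the existing checks can find.** Source data verification tests whether the eCRF agrees with the source. If a wrong strength is recorded identically in both, they agree. Only a comparison with weight and the chart shows that the strength was wrong. The accountability log can show which product was used, but no section asks for it to be compared with a child's weight.

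**3. Illustration (the true rates and recognised shares are assumptions, not in the documents).** Expected reported count = N × true error rate × share recognised, with N = 150 children, each counted once.

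| True rate | All recognised | Half recognised | A quarter recognised |
|---|---|---|---|
| 2% | 150 × 0.02 = 3 | 1.5 | 0.75 |
| 5% | 150 × 0.05 = 7.5 | 3.75 | 1.9 |
| 10% | 150 × 0.10 = 15 | 7.5 | 3.75 |

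A count of 3.75 thus fits a true rate of 5% with half recognised, or 10% with a quarter recognised. If no error is reported, the exact two-sided 95% upper limit is 1 − 0.025^(1/150) = 2.4%, and it applies to reported errors only. Dividing by the share recognised gives 2.43% / 0.5 = 4.9% or 2.43% / 0.25 = 9.7% for true errors.

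**4. Adverse events.** Only doses above the prescribed one count as overdoses under section 6.3.2. Underdoses have no such second route. A child with any other adverse event is already in the proportion. Assuming 9 true errors (6% of 150), 70% of them unrecognised and half of those overdoses, 9 × 0.7 × 0.5 = 3.15 children, or 3.15 / 150 = 2.1 percentage points, is the most that proportion would lose.

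**5. A conflict over what is counted.** Section 4.3.6 gives failing to switch nostrils as an example of an error. Sections 6.2.2 and 7.4.2 count only deviations that change the dose, which nostril order does not do by itself.

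**The case against.** The strongest reply is that the plan contains several safeguards. The monitor verifies the accountability log, reviews IMP handling and verifies source data; the eCRF has logic checks that raise queries; a physician is present at dosing (section 1.7.1); and overdoses are recorded as adverse events. Any of these could bring an unnoticed error to light, and nothing prevents site staff from then reporting it. A reader might infer that an error the giver did not notice can never enter the count. The documents do not support that: they leave the cross-check unstated; they do not rule it out.

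A reader might also infer from the absence of a medication-error row in Table 1 that the data are not collected. That is a matter of layout. Additional analgesics have no row of their own either and are covered by a footnote to concomitant medication.

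Much is also unseen. The dosing text is partly redacted, the Table 2 chart is not visible, and the IMP manual, the eCRF specification and the separate SAP announced in section 7 are not part of the text available. Strength and sprays may already be captured per dose.

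Finally, a programmed check works on what staff enter. Sprays miscounted by the person who records them would pass it.

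These replies limit how strongly the point can be put, and the last limits the remedy. What remains is that every section naming a source names the same one, and that no section compares dose given with weight and chart for this endpoint.

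**Conclusion.** The point holds as a gap in ascertainment. Feedback from the staff who give the IMP is the only named source for an endpoint defined by departure from the planned dose, and no stated cross-check uses the recorded weight or the accountability log. Errors that staff do not recognise may be missed, chiefly a wrong strength for weight or a misread chart, and the direction of the bias is downward. Unrecognised overdoses may also be missed as adverse events.

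The size cannot be estimated. A reader might want to state what share of errors is lost, but that share is simply one minus an assumed recognition rate; the figures in the working show sensitivity and are not estimates. The endpoint is secondary and descriptive, so no test or decision rule in the plan depends on it. The conclusion rests on the visible text: if the IMP manual, eCRF specification or separate SAP already contains the comparison, the protocol need only cite it.

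**What to change.** In sections 4.3.6 and 6.2.2, define the endpoint as the combination of:

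1. errors reported by site staff, as now; and
2. errors derived by a programmed check of the strength and number of sprays recorded for each dose in the eCRF against recorded weight and the Table 2 dosing chart.

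The monitor should reconcile strength and product used with the accountability log that is already verified under section 5.5. Report the two sources separately in section 7.4.2, so that the staff-reported count stays visible, and record any derived overdose as section 6.3.2 already requires. Reconcile sections 4.3.6 and 6.2.2 on whether failing to switch nostrils is an error, so that all sites count the same thing.

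The cost is a few eCRF fields, one program and no extra staff. If strength and sprays are already captured, only the derived check needs adding. The reported error count may rise. Two limits should be stated: the check will not find sprays miscounted by the person recording them, and where weight was estimated it tests consistency with the estimate, not with the child's true weight.
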